4.8 Unanticipated Problem Reporting

There are other types of incidents, experiences, and outcomes that occur during the conduct of human subjects research that represent unanticipated problems but are not considered adverse events. For example, some unanticipated problems involve social or

economic harm instead of physical or psychological harm associated with adverse events. In other cases, unanticipated problems place subjects or others at increased risk of harm, but no harm occurs. If an unanticipated problem occurs that does not involve an adverse event, it will still be reported to the DSMB and the IRB under HHS regulation 45 CFR Part 46 ([Unanticipated Events HHS Policy](#)).

5. Study Outcomes

The study will have one primary outcome and three secondary outcome measures for the three specific aims. The primary outcome is change in SBP 12 months after the start of the intervention. The secondary outcomes are change in DBP 12 months after the start of the intervention, the number of medication changes as a measure of treatment intensification, and the additional cost of the intervention.

Aim 1: Determine if our intervention leads to decreases in SBP.

Our working hypothesis is that there will be greater decreases in both SBP and DBP among the pharmacist-intervention group than among controls. We will compute the change in SBP for each subject at 12 months compared to their initial SBP. The SBP readings will be collected at enrollment and at 12-months by research assistants. The primary outcome measure for Aim 1 will be the difference in mean SBP between the control and intervention groups at 12 months.

Aim 2: Determine if our intervention leads to intensification of therapy.

Our working hypothesis is that there will be a greater number of medication changes in the intervention group compared to the control group. We will count the number of medication changes (dose increased, dose decreased, drug stopped, drug started) during the 12 months following the start of the intervention. The total number of medication changes will be the primary outcome measure for Aim 2. In addition, we will determine the number of pharmacist recommendations that were accepted by physicians. These are process measures: we found in our previous studies that BP improvement was primarily related to medication changes. We are assuming that changes are a sign of close monitoring. Indeed, we have used this measure previously. However, we realize that not all medication changes are equal, and thus we will record both medication trends and final treatment for each patient.

Aim 3: Determine the cost effectiveness of the intervention.

Our working hypothesis is that our intervention will be cost effective when compared to the control group. In addition, we will compare these results to previous pharmacist interventions. Because much pharmacist time is spent on non-direct patient care activities, we are convinced that our bi-directional texting approach will be both labor and cost saving. We will compute the incremental cost effectiveness ratio (ICER) using the total costs of doctor visits, pharmacist time, medications and medication changes during the 12 months of the trial. The ICER will be the difference between the control and intervention groups in average total cost

divided by the difference in average decrease of SBP and DBP. The ICER will be expressed in the dollars per mmHg reduction in BP and will be the primary outcome in this Aim.

6. Statistical Design and Power

Aim 1 Analysis: The analysis will be done on an intent-to-treat basis regardless of the number of reported BP readings or the number of pharmacist interactions with the participant. Our primary outcome will be a comparison of mean SBP values at 12 months. We will use linear mixed effects models (LMMs) with BP as the outcome. We will explore the timing of the change by also evaluating BP at 6 months. To test the intervention, we will include time (baseline, 6 month, 12 month) as a fixed effect factor and its interaction with treatment arm. We will use random effects for clinic and physician nested within clinic to account for practice heterogeneity between clinics and providers. Temporal correlation will be accounted for by using an autoregressive error structure. Specifically, the model will be given as

$$\begin{aligned}
 BP_{cpit} &= \tau_t + \alpha_c + \gamma_{cp} + (\omega_t + \nu_{tc} + \xi_{tcp})X_{cpi} + \epsilon_{cpit}, \\
 c &= 1, \dots, C, \quad p = 1, \dots, P_c, \quad i = 1, \dots, n_{cp}, \quad t \in \{0, 6, 12\}, \\
 (\alpha_c, \gamma_{cp})' &\stackrel{\text{iid}}{\sim} N(0, G_1), \\
 (\nu_{0c}, \nu_{6c}, \nu_{12c})' &\stackrel{\text{iid}}{\sim} N(0, G_2), \\
 (\xi_{0cp}, \xi_{6cp}, \xi_{12cp})' &\stackrel{\text{iid}}{\sim} N(0, G_3), \\
 (\epsilon_{cpio}, \epsilon_{cpis}, \epsilon_{cpis})' &\stackrel{\text{iid}}{\sim} N(0, R),
 \end{aligned}$$

where C is the number of clinics, P_c is the number of providers within the c^{th} clinic, n_{cp} is the number of subjects recruited under the p^{th} provider in the c^{th} clinic, $BP_{(cpit)}$ is the blood pressure at time t for the i^{th} subject under the p^{th} provider within clinic c , τ_t is the control mean at time t , α_c and γ_{cp} are the random control effects for the clinic and provider-nested-within-clinic respectively, ω_t is the treatment effect at time t , ν_{tc} and ξ_{tcp} are the random treatment effects for the clinic and provider-nested-within-clinic respectively, X_{cpi} equals 1 if the i^{th} subject under the p^{th} provider within clinic c is assigned to the treatment group and zero otherwise, ϵ_{cpit} is the (auto-correlated) noise term, and G_1 , G_2 , G_3 , and R are covariance matrices for the random effects. This model will also be estimated for DBP.

Second, transition to control for patients who were uncontrolled at their baseline visit will be modeled using a generalized linear mixed effects model (GLMM) based on the Bernoulli distribution with a logistic link. We will test the intervention by including a fixed-effects term for the treatment assignment (intervention versus control). As before, we will include random effects for provider nested within clinic. Specifically, the model will be

$$\begin{aligned}
 \text{logit}(\mathbb{P}(Z_{cpio} = 1 | Z_{cpis} = 0)) &= \tau + \alpha_c + \gamma_{cp} + (\omega + \nu_c + \xi_{cp})X_{cpi}, \\
 (\alpha_c, \gamma_{cp})' &\stackrel{\text{iid}}{\sim} N(0, G_1), \\
 (\nu_c, \xi_{cp})' &\stackrel{\text{iid}}{\sim} N(0, G_2),
 \end{aligned}$$

where Z_{it} equals 1 if the i^{th} subject under the p^{th} provider within clinic c is controlled at time t , $t \in \{0, 6\}$, and zero otherwise.

Third, we will assess the duration of the change by modeling the odds of having controlled BP at 12 months among those uncontrolled at baseline but controlled at 6 months using a GLMM similar to that described above. All three models will contain any covariates (e.g., age, sex) that were not sufficiently addressed through randomization. In all analyses, the random effects incorporated into the final model will be chosen via Akaike Information Criterion with correction for small sample sizes (AICc).

Power: Based on prior work with the CAPTION trial, we expect a mean decrease in SBP of 17.3 (SD = 17.7) mmHg in the intervention arm and a decrease of 11.6 (SD = 18.2) mmHg in the control arm. We expect a difference of 5.65 mmHg between the groups with an expected pooled standard deviation of 17.9 with equal sized groups. In order to have 90% power to detect a difference of 5.7 mmHg or larger decrease in SBP with a Type I error rate of 5% and a standard deviation of 17.9 mmHg, we would need 180 subjects per arm or 360 subjects total.

In preliminary work in the CAPTION trial, 13.4% of control subjects dropped out or were lost to follow-up. 14.0% of subjects dropped out of the intervention arm during the first 9 months. In order to retain power after reasonable attrition rates over 12 months, we will recruit an additional 14% in each group to ensure we have at least 85% power. In addition, the sample size should be slightly increased to accommodate the interim analyses. This increases our total sample size to 420.

One interim analysis is planned after outcome data are received and the results are reported to the Data Safety and Monitoring Board from the first half of the study. The interim monitoring method of Lan and DeMets will be used with O'Brien-Fleming alpha spending function for the interim analyses. Accordingly, type I error rate of 0.00305 for the interim analysis and 0.4695 will be used for the final analyses. The current sample size of 420 patients total accommodates the interim analyses.

Aim 2 Analysis: The analysis will be done on an intent-to-treat basis regardless of the number of reported BPs or the number of pharmacist interactions with the subject. Our primary outcome will be the number of medication changes over 12 months in the control and intervention groups. We will use a GLMM based on the Poisson distribution with a log link function, and as in Aim 1 we will incorporate random effects for clinic and physician nested within clinic to account for practice heterogeneity between clinics and providers. As the observed treatment effects in those clusters are likely to be non-independent, we will include both random intercepts and random treatment effect for the intervention factor. Specifically, the model will be given as

$$\begin{aligned} \log(\mathbb{E}(Y_{cp})) &= \tau + \alpha_c + \gamma_{cp} + (\omega + \nu_c + \xi_{cp})X_{cp}, \\ (\alpha_c, \gamma_{cp})' &\stackrel{\text{iid}}{\sim} N(0, G_1), \\ (\nu_c, \xi_{cp})' &\stackrel{\text{iid}}{\sim} N(0, G_2), \end{aligned}$$

where Y_{cpi} is the number of medication changes for the i^{th} subject under the p^{th} provider within clinic c . The random effects incorporated into the final model will be chosen via AICc.

Power: Based on existing work, we expect an average of 4.9 medication changes in the intervention group (SD = 5.1) and an average of 1.1 medication changes in the control group (SD = 1.6). We would expect a difference of 3.8 changes per year with a pooled standard deviation of 3.8. In order to have 85% power to detect a difference of 3.8 or more changes with a Type I error rate of 5% and a standard deviation of 3.8, we would need 19 subjects per arm or 38 total. Considering both 14% loss to follow-up and adjusting the type I error rate for interim analysis, power of the study with our sample size of 420 will be more than adequate.

Aim 3 Analysis: The analysis will be performed on an intent-to-treat basis regardless of the number of reported BP measurements or the number of pharmacist interactions with the subject. The perspective of this cost analysis is society in general. For each patient encounter, pharmacists will record the number of minutes spent in the following activities: medical record review, consultation, patient assessment, ordering medications, medical education, lifestyle education, BP measurement education, making recommendations, and documentation in the medical record. Pharmacist costs will be estimated by multiplying the time spent by their compensation rate. Costs for clinic visits will be obtained from the university. Utilization measures will be converted to costs per subject using the Medicare fee schedule for visits. Pharmacist and physician salaries will be obtained from the Bureau of Labor Statistics. The average wholesale drug cost for prescription medications will be obtained from Lexicomp Online (<https://online.lexi.com>). Generic prices will be used when available. The drug cost per prescription for each subject will be calculated by multiplying the average wholesale price (AWP) by frequency and dose.

We assume that subjects in the intervention and control groups will have similar characteristics. However, if there are significant differences between the subjects in these groups, costs will be predicted using a multivariate generalized linear model with a gamma family and a log link to control for these differences.

We will determine the cost of the intervention by subtracting the average total cost (pharmacist, clinic, and drugs) for the intervention group from the average total costs for the control group. The ICER is calculated as the cost differential from the intervention divided by the outcome differential from the intervention. Our primary outcome will be average decrease in SBP, and the outcome differential will be the average decrease in SBP for the control group minus the average decrease in SBP for the intervention group. The result of this analysis will be an ICER, which gives the additional cost of the intervention per mm Hg of SBP decrease.

We will conduct at least two sensitivity analyses. Because the drug costs (average wholesale prices) from Lexicomp often overstate the actual prices paid by insurance companies and patients, we will adjust our drug costs and re-estimate our cost-effectiveness analysis. Specifically, the Kaiser Family Foundation estimates that average wholesale prices are, on average 17% higher than weighted acquisition costs for brand-name drugs, and 80% higher for generic drugs. In addition, pharmacist time can be represented by either wages per hour, or the

amount that pharmacists can bill Medicare for each activity. We will consider both ways to measure the value of pharmacists' time.

7. Data Safety and Monitoring

All procedures and protocols will be developed by the PIs and the study coordinator with protection of the participants and data as the highest priority. All procedures will be reviewed by the University of Iowa IRB as well as the Data and Safety Monitoring Board prior to being implemented (additional information about DSMB members and responsibilities can be found in the DSMB Charter). The study coordinator will thoroughly train and monitor all research interns during the course of the study and will be available to answer questions via phone when not in the clinic.

8. Study Responsibilities

By signing this protocol, the study's two PIs agree to be responsible for implementing and maintaining quality control and quality assurance systems to ensure that all work incidental to this protocol is conducted and data are generated, documented, and reported in compliance with the protocol, with accepted standards of Good Clinical Practice (GCP), and with all applicable federal, state, and local laws, rules, and regulations relating to the conduct of the clinical study.

Once the study activities are completed, the PIs will be primarily responsible for creation, review, and submission of publications and presentations relating to major aspects of the study and approved analyses within a timely fashion.

The manuscript containing the overall study results will be distributed to all study investigators at the University of Iowa for review and comment before submission to a peer-reviewed journal with a reasonable period for review, but the final content will be at the discretion of the PIs. Any other manuscripts containing these data, including abstracts, will be distributed to all relevant study investigators who are participating on such publications before submission, with a reasonable period for review. Submitted publications will conform to international standards for biomedical manuscripts, including those regarding authorship.

9. Ethical Considerations

By signing this protocol, the PI agrees to conduct the study in compliance with the protocol; the Declaration of Helsinki; and all applicable federal, state, and local laws, rules, and regulations relating to the conduct of the clinical study.

The University of Iowa has overall responsibility for the conduct of the study, including assurance that the study meets the sponsor's regulatory requirements.

The PIs have both ethical and legal responsibility to ensure that each subject being considered for inclusion in this study is given a full explanation of the study. Informed consent will be obtained from all subjects before any data are collected and before any study-related procedures are performed. Before and after subject provision of informed

consent, research team members will be available via email or phone to answer questions or concerns regarding procedures and risks.

Subject confidentiality will be maintained throughout the clinical study. Subject information collected in this study will comply with the standards for protection of privacy of individually identifiable health information as promulgated by HIPAA and as mandated in Title 45 CFR Parts 160 and 164. All records will be kept confidential, and the subject's name will not be released to non-authorized persons or entities at any time. Subject records will not be released to anyone other than members of the research team at each site who have a need for such information, and responsible regulatory authorities when requested. In all cases, caution will be exercised to assure the data are treated confidentially and that the subject's privacy is guaranteed.

Hard copy records containing subject data collected at sites (informed consent documents) will be stored in a locked cabinet in a locked office. Identification numbers will be used in place of names on report forms. All electronic study data will be stored on encrypted, password-protected servers located within security firewalls, such that only members of the research team who need access will be allowed access to study files. Subject data will not be reused or disclosed to any other person or entity, except as required by law, for authorized oversight of the study, or for other research for which disclosure of the requested data would be permitted by the HIPAA Privacy Rule. If needed, any transport of electronic data will occur via a password-protected disk or secure transfer protocol.

All subjects will consent, through their IRB-approved informed consent document to release of protected health information to the University of Iowa research teams as part of the consent process.

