Study Title: A Pharmacist Intervention for Monitoring and Treating Hypertension Using Bidirectional Texting

Version Number/Amendment	Approval Date
Original Protocol, Version 1.0	8/3/2019
Revised Protocol, Version 2.0	11/27/2019
Revised Protocol, Version 3.0	12/30/2019
Revised Protocol, Version 4.0	7/17/2020
Revised Protocol, Version 5.0	9/21/2020

Protocol Synopsis

Protocol Title	A Pharmacist Intervention for Monitoring and Treating Hypertension Using Bidirectional Texting
Main Criteria for Inclusion	Clinic measured blood pressure of ≥ 145 mmHg or ≥ 95 mmHg at two previous clinic visits or one previous clinic visit and on the day of enrollment. Previous clinic visit BPs must be within the past 18 months and measured at least 2 weeks apart from each other.
Study Objective	To evaluate whether our scalable SMS approach combined with a pharmacist-based intervention improves BP management and that is cost effective.
Study Design	A single-site, two-arm, single-blind randomized trial
Number of Sites	1 site, 3-4 clinic locations
Study Arms	2 Study Arms a) Intervention Group- Text 7 morning and 7 evening BP values at baseline. Monitored by a study pharmacist for 12 months. Research visits at 6 and 12 months b) Control Group- Text 7 morning and 7 evening BP values at baseline. Research visits at 6 and 12 months
Total Number of Subjects	420
Duration of Study Participation	12 months
Primary Outcomes	Mean difference in systolic blood pressure between the control and intervention groups at 12 months.
Secondary Outcomes	Mean difference in diastolic blood pressure between the control and intervention groups at 12 months. Total number of medication changes (i.e., dose, discontinuation, initiation, etc.) from baseline to 12 months.

	Total cost of medications, time spent by research staff, and clinic visits per patient from baseline to 12 months.

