- Purpose of the research study, duration of study participation, and the number of research visits and study contacts (i.e., texting, phone calls, emails) required.
- The study procedures and requirements.
- The risks of the study.
- The voluntary nature of the study. The participant may drop out of the study at any time.
- That their decision to participate or not will have no effect on their relationship with or care from their physician or on the clinical care that they receive.
- HIPAA information: The research team must have access to the participant's medical information and to create medical information in order for the participant to be in the study; the investigators will obtain medical record data for the time period that spans 18 months preceding enrollment until 12 months following enrollment.
- The research-related injury section.
- Contact information that participants can use to reach investigators for study-related issues.

If the patient agrees to participate, they will be asked to sign two copies of the consent form. The research intern will sign the consent forms as the witness. One copy will be given to the participant and one copy will be kept and filed securely in the research team office. The patient will be enrolled in the research study in the electronic medical record via IRB and hospital policy.

Patients may take an unsigned consent form with them to think about participation. They will be given contact information to schedule a follow-up appointment with an intern at a later date if they choose to participate.

Patients may also sign the consent form but schedule completion of other baseline activities for a later date to meet their scheduling needs.

The English and Spanish consent forms are provided in Appendix 4.

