All participants will be asked to return to the clinic where they enrolled at for a 6-Month appointment with a research intern. To allow for flexibility with scheduling, 6-Month appointments will be allowed to occur anytime between 5 Months and 7 Months after the enrollment date. This BP value will be the outcome BP value. If a participant is not able to make it to the clinic during this window, but does want to come in after the 7 Month date, this will be allowed and all data will be collected, however, it will not be counted in the 6-month outcome and the 6-month outcome will be considered missing. In this case, a note will be placed in the participant's record and these data may not be used in analyses.

At the 6-Month appointment, the research intern will collect the research BP values, any BP medications that the participants are currently taking, the last 3 BP values that were

recorded by the participant's home BP cuff, and test the home BP cuff for accuracy. If the home BP cuff appears to be measuring inaccurately, it will be replaced. The participant will be sent another \$50 compensation check. All of the procedures outlined at baseline will be followed again, but the data will be collected on separate 6 Month REDCap forms (not shown).

4.6 12-Month Visit Procedures

All participants will be asked to return to the clinic for a 12-Month appointment with a research intern. To allow for flexibility with scheduling, 12 Month appointments will be allowed to occur anytime between 11 Months and 13 Months after the enrollment date. If a participant is not able to make it to the clinic during this window, these data will be missing.

At the 12-Month appointment, the research intern will collect the research BP values, any BP medications that the participants are currently taking, a 12-Month Exit Survey (Appendix 11) asking for the participant's feedback about the study, and send another \$50 compensation check. All of the procedures outlined at baseline will be followed again, but the data will be collected on separate 12-Month REDCap forms (not shown). Participants will also be asked about any hospitalizations or emergency room visits that occurred over the 12-month follow up period, especially those that occurred outside of the University of Iowa system (Appendix 12).

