Appendix 2: Study Procedures Timeline

Time	Activity	Control Group	Intervention Group
Day 0	Screening Consent Baseline Appointment	X	X
Day 1 – Days 7-15	Home BP measured and returned via text message	X	X
Days 7-15 – Day 18	Participants randomized; Pharmacists review home BP values, contact participants	X	X
Day 18 – 6 Months	Participants text home BP values 3 days per month Pharmacists monitor BP, adjust treatment as needed		X
6 Months	Participants return to clinic for appointment	X	X
6 Months – 12 Months	Participants text home BP values 3 days per month Pharmacists monitor BP, adjust treatment as needed		X
12 Months	Participants return to clinic for appointment	X	X

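### The Aim 2 medication-change count has two conflicting windows: one admits changes made before randomisation, the other runs past the described record access

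*Combined protocol and SAP*

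**What the plan says.** Three time origins appear in the protocol.

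- **Start of the intervention.** Section 5 states: "The primary outcome is change in SBP 12 months after the start of the intervention". For Aim 2 it counts dose increases, dose decreases, stops and starts "during the 12 months following the start of the intervention". No section defines this start or says what it means for a control participant, who has a single pharmacist contact (section 4.4.1).
- **Baseline.** The Synopsis lists as a secondary outcome "Total number of medication changes (i.e., dose, discontinuation, initiation, etc.) from baseline to 12 months".
- **Enrolment.** Section 4.6: "12 Month appointments will be allowed to occur anytime between 11 Months and 13 Months after the enrollment date". Section 4.5 uses the same origin for the 6-month visit. In section 4.2, the intern's explanation of the HIPAA terms gives a period of record access that "spans 18 months preceding enrollment until 12 months following enrollment".

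Section 4.1 places randomisation after the home readings, which end at 14 readings or 15 days. Appendix 2 puts screening, consent and baseline on Day 0. Its row "Participants randomized; Pharmacists review home BP values, contact participants" runs from Days 7-15 to Day 18 and is marked for both arms.

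Section 6 analyses Aim 2 with a Poisson mixed model with a log link. The model has no follow-up-time offset.

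**The concern.** A count outcome needs a stated start and end. Here the two stated windows start on different days, and each has its own fault.

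The Synopsis window opens before randomisation. Section 4.2 recruits people with elevated clinic BP at scheduled clinic appointments, so a physician may well change treatment that same day. Such a change cannot be an effect of the intervention, yet it would count as an outcome event. With a log link the treatment effect is a ratio, and adding similar counts to both arms moves that ratio toward 1. This is dilution of the estimate, not only added noise.

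The section 5 window opens later and closes 12 months after that, which is past the record access that section 4.2 describes. The tail may go unobserved.

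At stake are the size and reproducibility of the Aim 2 estimate: two analysts following two parts of the same protocol would obtain different counts.

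**Working it through.** **Inputs.** Planned means of 4.9 (intervention) and 1.1 (control) changes, difference 3.8, pooled SD 3.8, 19 per arm for 85% power (section 6, Aim 2). Gap from Day 0 to randomisation of 7 to 18 days (Appendix 2). Record access to 12 months after enrolment (section 4.2). One year = 365.25 days; one month = 30.44 days.

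**1. The plan's own figures.** Difference: 4.9 − 1.1 = 3.8. Normal-approximation sample size: n = 2(1.960 + 1.036)² × (3.8/3.8)² = 17.95, so 18 per arm, within one of the stated 19. Planned rate ratio: 4.9/1.1 = 4.45.

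**2. Synopsis window.** Let d be the mean number of pre-randomisation changes per participant, equal in the two arms because it precedes allocation. The documents give no value for d, so a range is assumed. Ratio = (4.9 + d)/(1.1 + d).

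| d (assumed) | Calculation | Ratio |
|---|---|---|
| 0 | 4.9/1.1 | 4.5 |
| 0.1 | 5.0/1.2 | 4.2 |
| 0.3 | 5.2/1.4 | 3.7 |
| 0.5 | 5.4/1.6 | 3.4 |

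The absolute difference stays at 3.8 throughout. The table takes 4.9 and 1.1 as the counts after randomisation.

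**3. Section 5 window.** If enrolment is Day 0, the window ends 7 to 18 days after record access does.

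- Share of the window: 7/365.25 = 1.9%; 18/365.25 = 4.9%.
- Changes in an 18-day tail at an even rate: 4.9 × 18/365.25 = 0.24 (intervention); 1.1 × 18/365.25 = 0.05 (control).
- Loss in the difference: 3.8 × 18/365.25 = 0.19.
- Sample size after that loss: 17.95/(1 − 0.0493)² = 19.9, so 20 per arm, against 420 planned in total.
- Rate ratio: equal proportional truncation leaves it at 4.45.

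**4. Visit timing.** The gap is 7/30.44 = 0.23 to 18/30.44 = 0.59 month. The 11 to 13 month visit window is therefore 10.77 to 12.77 months after a Day 7 start, or 10.41 to 12.41 months after a Day 18 start. Twelve months after the start stays reachable unless the gap exceeds one month, about 30 days.

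**The case against.** The strongest reply is that this is a small wording inconsistency. Both arms are randomised and contacted at the same point, so controls have a natural equivalent origin. The gap is 7 to 18 days, and Aim 2 has far more participants than it needs. Lost changes are not established either. Interns record current BP medications at study visits, and pharmacist forms log change type and outcome date in the intervention arm (Appendix 10). Pharmacist contact is about every 2 weeks while BP is uncontrolled and can fall to every 2 months afterwards (section 4.4.2). Changes are therefore likely to come early, which makes 0.24 an upper figure. The access limit is known only from the protocol's summary, because the consent forms are not available here.

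Most of this stands, and it makes the section 5 tail minor. It does not answer the dilution under the Synopsis window, which depends on how many changes occur before randomisation rather than on how many days pass. Nor does visit data cure it. A list of current medications does not date a change, and the chart review in section 4.6 lists visits, emergency visits and hospitalisations only.

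A reader might infer more from the same passages; the documents do not support it:

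- **That follow-up is shorter than stated, or that the SBP result is biased.** The visit window still reaches 12 months after the start, an early visit is mostly ordinary window width, and both arms shift together.
- **That delayed baseline procedures stretch the gap to many weeks.** Section 4.2 does allow this: "Patients may also sign the consent form but schedule completion of other baseline activities for a later date". But it lengthens the gap only if enrolment is dated at consent. Section 4.1, section 5 and Appendix 2 tie enrolment to the baseline visit.
- **That Aim 3 costs are cut short.** Costs are never defined from the start of the intervention. The Synopsis runs them from baseline, and section 5 refers only to the trial's 12 months.

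**Conclusion.** The point holds for the Aim 2 count window. The Synopsis and section 5 give different windows, and the start in section 5 is undefined, most plainly for controls.

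The Synopsis window could lower the planned ratio of 4.5 to between 4.2 and 3.4. This rests on an assumed 0.1 to 0.5 pre-randomisation changes per participant, equal between arms, and on the planned means describing the period after randomisation. The section 5 window leaves 1.9% to 4.9% of the year outside the described access. That is at most about 0.24 against 0.05 changes per participant if changes are spread evenly, with no effect on the ratio if both arms lose the same share.

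The primary SBP comparison is not biased, and power is essentially unaffected. For SBP only the wording needs correcting.

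**What to change.** 1. Define time zero for the Aim 2 count, in both arms, as the randomisation time stamp that the website already stores (section 4.4). Exclude changes dated before it.
2. End the count at a point inside record access, for example 12 months after enrolment, and add log follow-up time as an offset to the Poisson model. With a 7 to 18 day gap, follow-up is about 358 to 347 days (365.25 − 7 and 365.25 − 18). Alternatively, extend record access for new participants so that a full 12 months from randomisation is covered.
3. Align the Synopsis and section 5 with this rule. Reword the primary and DBP outcomes, now set at 12 months from the start of the intervention, to match the visit windows actually used. Visits need not be re-anchored.

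The cost is protocol wording, one model term and, only if access is extended, a change in consent language. The one practical demand is that each medication change carries a date in both arms. The pharmacist forms provide an outcome date for the intervention arm. The medication form in Appendix 6 has no date field for a change, so a source for dated changes in controls must be named.
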